4. METHODS: ASSIGNMENT OF INTERVENTIONS

4.1 Randomization and Allocation Concealment

A web-based randomization system through REDCap maintained at the University of Alberta (Edmonton, Alberta) will be used to allocate treatment assignments for all participating sites. The randomization process will consist of a computer-generated random listing of the treatment allocations, stratified by site and using variable permuted blocks of 2, 4 and 6. All investigators, research staff and clinical personnel will be blinded to the allocation schedules.

4.2 Implementation

Patients will be identified and enrolled in the WISDOM trial by ICU physicians (attending physicians, fellows, residents) and research personnel. The allocated intervention will be communicated to the most responsible care team member, who will co-sign the trial-specific standardized order sets and prescribe the allocated intervention. The allocated intervention will be implemented by the bedside nursing personnel delivering the CRRT.

4.3 Blinding

The WISDOM pilot trial is designed as a prospective, randomized, open-label, blinded endpoint (PROBE) trial.[36] This approach is necessary given the impracticality of blinding the prescription and delivery of CRRT. PROBE trials produce comparable effect estimates to conventional double-blind trials, however, are more pragmatic and have greater similarity to standard clinical practice.[37] In this trial, process measures of performance and safety endpoints will be independently ascertained.

5. METHODS: ANALYSIS

5.1 Proposed analyses

Baseline characteristics will be summarized with descriptive statistics. The primary feasibility endpoint, the difference in mean (SD) CRRT dose-intensity between groups, will be reported as difference in means (with 95% confidence intervals [CI]). For secondary feasibility, physiological and biochemical, and process of care endpoints, all

continuous variables will describe the number of non-missing values [n], means, medians, standard deviation [SD], interquartile ranges, whereas all categorical variables, will describe frequency counts and percentages, as appropriate. Between group differences will be assessed using Chi-square or Fisher's exact tests for dichotomous outcomes and student t-tests or non-parametric methods for continuous outcomes, as appropriate. A mixed linear regression for repeated measures will be performed, adjusted for baseline variables and CRRT duration, to evaluate dose-intensity differences by allocated group. Safety endpoints will describe and compare the occurrence of AE, SAE and SAE leading to intervention discontinuation overall and by allocated CRRT dose-intensity.

The WISDOM pilot trial is not designed and will be inadequately powered to detect important differences in clinical outcomes and effect estimates may be inaccurate with large confidence intervals.[34]

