3.5 Outcomes

3.5.1 Primary Endpoint

The primary feasibility endpoint is the difference (95% CI) in the total delivered effluent flow rate per patient between those in the lower and standard CRRT dose-intensity groups. The WISDOM pilot trial will target the detection of a minimum difference of 10

mL/kg/hr in average delivered dose-intensity between the groups. This will be an important proof-of-concept endpoint to inform the feasibility of a larger multi-centre trial.

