3.5.3 Biochemical Endpoints

The biochemical endpoints will assess the tolerability of the intervention and are:

- i) daily serum sodium, bicarbonate, base excess, strong ion difference (SID) and pH while receiving CRRT and number of (%) days without severe acidemia (pH <7.25).
- ii) daily serum magnesium, potassium, and phosphate while receiving CRRT and number of (%) days without hyperkalemia (K^+ >5.5 mmol/L).
- iii) daily serum urea while receiving CRRT and number of (%) days without serum urea >35 mmol/L.

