3.6 Sample size calculation and recruitment

For the WISDOM pilot trial, our primary sample size consideration will address the detection of a minimum difference in the delivered dose-intensity of CRRT between the groups. For the WISDOM pilot trial, we are targeting a total sample size of 100 patients (50 patients per group). This is based on the ability to detect a minimum difference of 10 mL/kg/hr in dose-intensity, assuming delivery of 25 mL/kg/hr in the standard dose-intensity group and 15 mL/kg/hr in the lower dose-intensity group, with a conservative standard deviation (SD) of 15, 90% power, and an alpha of 0.05. This would translate into a sample of 96 patients (48 patients per group) that will be inflated to 100 to account for any withdrawal or dropout (See Table below).

Table. Sample Size Calculation Estimates.

Scenario	Difference in Dose Intensity	Standard Deviation	Power	Estimated Sample (Total)
1	10	5.0	0.9	12
2	10	7.5	0.9	24
3	10	10.0	0.9	44
4	10	12.5	0.9	66
5	10	15.0	0.9	96
6 (ATN Trial)	15	6.3*	0.9	18
7 (RENAL Trial)	15	15.3**	0.9	100
* From the ATN trial, based on average standard deviation for both groups of the aggregate total effluent flow rate delivered.[18]				
** From the RENAL trial, based on average standard deviation for both groups of the aggregate total effluent flow rate delivered.[17]				

For the WISDOM pilot trial, the total sample of 100 patients would translate into a target recruitment of 4 patients per week (50% of expected eligible) across 5-10 sites, thereby requiring an estimated 6-10 months to complete, if all sites are active.

We will further explore the practicality of identification of eligible patients, site-specific recruitment, protocol adherence, and data monitoring and ascertainment, that will inform the logistical planning and operations of a larger-scale multi-centre trial.[34]

All patients enrolled in the trial will be admitted to and monitored in an ICU setting. The primary and secondary feasibility endpoints, along with biochemical and process of care endpoints will be captured in local hospital medical records (either paper charts or electronic medical records) and data repositories. Data will be captured electronically where feasible, otherwise, standardized paper case report forms will be used. The expected rate of loss to follow-up will be low for ICU and hospital-specific outcomes

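### Randomization is stratified by site, but the stated primary dose comparison has no site term, so its 95% CI may be wider than necessary

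*Protocol*

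**What the plan says.** Section 4.1 describes allocation as "stratified by site and using variable permuted blocks of 2, 4 and 6". The primary endpoint in section 3.5.1 is one quantity per patient, the "total delivered effluent flow rate per patient". Section 5.1 says the between-group difference in mean dose-intensity "will be reported as difference in means (with 95% confidence intervals [CI". No site term is named there or anywhere else in section 5.

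The same paragraph adds a second dose analysis: "A mixed linear regression for repeated measures will be performed, adjusted for baseline variables and CRRT duration, to evaluate dose-intensity differences by allocated group". The baseline variables are not listed, site is not mentioned, and this model is not designated the primary analysis.

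For the other continuous endpoints, section 5.1 names "student t-tests or non-parametric methods for continuous outcomes, as appropriate". These include the biochemical endpoints of section 3.5.3, which are recorded repeatedly (for example, "daily serum magnesium, potassium, and phosphate while receiving CRRT"). Some also have a count or percentage of days, as in "daily serum urea while receiving CRRT and number of (%) days without serum urea >35 mmol/L".

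**The concern.** Stratifying by site balances the arms within each site. If site also predicts delivered dose, the true sampling variance of the treatment difference contains only the within-site part. A two-sample interval is still computed from the total variance, so it overstates the uncertainty, and the precision gained from stratifying is not reported.

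The protocol gives some reason to expect site differences. Clearance mode and anticoagulation are left to the clinical team (section 3.4.4), several adjustments follow ICU-specific protocols (section 3.4.2), and sites range from academic to community units in Canada and abroad (section 3.2).

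The mixed model does not settle the matter. Besides not naming site, it conditions on CRRT duration, which is observed after randomization. Section 2.5 states that the trial program will ask whether the lower dose shortens that duration, so adjusting for it may distort the comparison of arms.

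The interval is itself the primary result of this pilot, so its calibration matters, although the error is on the safe side.

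**Working it through.** **Inputs from the protocol.** Difference 10 mL/kg/hr, "assuming delivery of 25 mL/kg/hr in the standard dose-intensity group and 15 mL/kg/hr in the lower dose-intensity group"; SD 15, power 90%, alpha 0.05, 96 patients raised to 100, 5-10 sites (all section 3.6); 518 patients with 2,790 CRRT-days (section 2.3).

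**Inputs assumed.** The between-site share of dose variance, ρ, from 0 to 0.3, and the within-patient correlation of daily laboratory values, from 0.3 to 0.7. The protocol gives neither.

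**Step 1: the plan's own figure.** For a two-sided test by normal approximation, n per group = 2(1.960 + 1.282)² × 15²/10² = 47.3, rounded up to 48, or 96 in total. This matches section 3.6, so the sample size rests on a comparison without site.

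**Step 2: interval without site.** At 50 per group, half-width = t(0.975; 98) × SD × √(2/n) = 1.984 × 15 × √(2/50) = 5.95 mL/kg/hr.

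**Step 3: interval with site.** With balance within site, the width ratio is roughly √(1−ρ), and the two-sample interval covers about 2Φ(1.96/√(1−ρ)) − 1. At ρ = 0.1 this gives 0.949 and 96.1%; at ρ = 0.3, 0.837 and 98.1%. A simulation allows for the small number of sites: 4,000 trials per setting, 100 patients, equal-sized sites balanced within site, total SD 15, true difference 10. It compares the pooled t interval with a linear model containing site indicators. Results for 10 sites:

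| ρ | Half-width without site | Half-width with site | Narrower by | Coverage without site |
|---|---|---|---|---|
| 0 | 5.94 | 5.95 | none | 95.5% |
| 0.05 | 5.94 | 5.80 | 2% | 95.6% |
| 0.1 | 5.90 | 5.62 | 5% | 96.2% |
| 0.2 | 5.87 | 5.31 | 10% | 96.9% |
| 0.3 | 5.87 | 4.98 | 15% | 98.0% |

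With site in the model, coverage stayed between 94.8% and 95.6%. With 5 sites the pattern is similar, with slightly smaller gains: 5.87 to 5.63 at ρ = 0.1 (4%) and 5.74 to 4.97 at ρ = 0.3 (13%).

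**Step 4: cost of the site term.** With 10 sites, residual degrees of freedom fall from 98 to 100 − 10 − 1 = 89. The ρ = 0 row shows the effect: 5.95 against 5.94.

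**Step 5: laboratory values, conditional case only.** Days per patient = 2,790/518 = 5.4. If patient-days were treated as independent, the design effect would be 1 + (5.4 − 1) × correlation, and the true type I error 2(1 − Φ(1.96/√design effect)). At correlation 0.3 the design effect is 2.32 and the error 19.8%; at 0.5, 3.20 and 27.3%; at 0.7, 4.08 and 33.2%. With one summary value per patient there is no such inflation.

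**The case against.** The strongest reply is that this is detail for the statistical analysis plan, which section 6.1 promises. The protocol never calls the primary comparison unadjusted, a regression with site also reports a difference in means, and site could be among the unlisted baseline variables of the mixed model. That is fair as far as it goes. However, section 5.1 does name the form of the primary result and section 4.1 does name the stratification factor. A later plan that follows section 5.1 literally would leave site out, and the mixed model is not presented as the primary analysis.

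The second reply is that the gain rests on an assumed site share. Both arms have weight-based delivered targets (section 3.4.1), and section 4.2 speaks of trial-specific order sets, although section 3.4.3 says local ones. Either feature could make the share small. The variable practice in section 2.3 describes routine care, not dosing under the trial. This stands: the gain may be close to nil. The cost is then also close to nil.

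A reader might infer that the laboratory comparisons carry a type I error of 20-33%. The documents do not support that. Nothing says patient-days are pooled as independent, the counts and percentages of days in section 3.5.3 can be read as per-patient summaries, and section 5.1 qualifies its tests by appropriateness. The figure describes a possible misuse, not the plan.

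**Conclusion.** The point holds as a modest loss of precision in the primary comparison. The stated interval is valid. If sites differ, it is wider than necessary by an amount that depends on a between-site share the protocol does not give: nothing at 0, about 2% at 0.05, and about 5-15% at 0.1-0.3, with coverage of about 96-98% over that last range. These figures assume SD 15, 100 patients and equal-sized sites balanced within site.

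A reader might go further and infer that the primary interval is wrong or that the feasibility conclusion is at risk. Neither follows. The error is conservative, the sample size of 96 was planned without site adjustment and reproduces, and a difference of 10 mL/kg/hr exceeds a half-width of about 6 with or without site. Nor is dose analysed only by a simple difference, since an adjusted repeated-measures model is also planned; it just does not supply the missing site term.

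For the daily laboratory values, the protocol leaves the unit of analysis open. That calls for a clarifying sentence and is not an error.

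**What to change.** In section 5.1 or the statistical analysis plan, before database lock:

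- **Primary comparison.** Estimate the difference in per-patient mean delivered dose, with its 95% CI, by linear regression on arm with site as a covariate (small sites pooled by a stated rule) or as a random effect. Label this as the primary analysis. The mixed model without site and with CRRT duration as a covariate should not stand in for it.
- **Daily laboratory values (secondary suggestion).** State either one summary value per patient, or the repeated-measures mixed model already planned for dose, with a patient effect, site and the value at randomization. The simple tests can stay for endpoints with one value per patient.

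The cost is two sentences and, for 5-10 sites, a few degrees of freedom. Sample size, data collection and trial conduct do not change.

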2.2 Why is the trial needed now?

No RCT to date has specifically evaluated the lower dose-intensity threshold for critically ill patients receiving CRRT though two pilot trials are ongoing (Clinicaltrials.gov: NCT6021288 and NCT06014801).

Overall, there has been no specific evidence or guidance on the minimum dose-intensity targets for patients receiving CRRT. This is important for several reasons. First, CRRT is an invasive, resource intensive and expensive therapy.[6] As such, there should be a concerted effort to minimize time on RRT and facilitate early recovery and weaning. Second, abundant evidence derived from secondary analyses have suggested that higher CRRT dose-intensity can propagate oliguria, prolong the need for CRRT and disrupt and delay kidney recovery.[21, 24] This would imply that lower dose-intensity may facilitate kidney recovery and earlier weaning from RRT. Third, evidence has emerged that higher dose-intensity may have non-renal organ support implications, such as risk of cardiac arrhythmias and delayed weaning from invasive mechanical ventilation.[25] Fourth, evidence derived from observational registries has shown that lower CRRT dose-intensity (~10-18 mL/kg/hr), aligned with the lower CRRT dose-intensity proposed herein, can provide comparable efficacy for azotemic, metabolic and acid-base control.[26-28] Observational data have suggested a prescribed CRRT dose-intensity of 15 mL/kg/hr is not associated with worse outcomes compared with guideline directed dose-intensity.[27, 28] This is lower quality evidence, however, implies that lower dose-intensity may be acceptable and safe. Fifth, it is plausible that following a short period of metabolic stabilization with CRRT (~12-24 hours), the minimum CRRT dose-intensity threshold currently recommended is excessive and has the potential for unmeasurable harm (e.g., excess removal of electrolytes, micronutrients, and medications [antimicrobials; antiepileptics; etc.]). Patients receiving CRRT for sustained periods of time (>48 hours) routinely require supplementation to replace the loss of electrolytes, protein and vitamins. Finally, a lower CRRT dose-intensity may have a meaningful impact on reducing bedside nursing workload (e.g., fewer replacement solution bag changes; less need for supplementation); reducing avoidable waste (e.g., reduce carbon footprint) and reducing costs attributable to CRRT (e.g., reducing total volume of replacement/dialysate solutions; shortening total CRRT duration)..[29]

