
2.3 How will the results of this trial be used?

While this proposal outlines a pilot feasibility trial, it is aimed at performing a larger rigorous RCT that will generate generalizable and high-quality evidence to impact clinical practice. The findings of the main phase of the WISDOM trial program will provide clearer evidence to guide the prescription of a minimal dose-intensity for patients receiving CRRT. Current practice in Alberta for the prescription of CRRT is variable. Based on data from October 1, 2023 to December 31, 2023, there were 518 patients receiving CRRT

across Alberta (2,790 CRRT-days; average 5.4 days per patient) and an estimated 77% of these patients receiving CRRT fulfilled the criteria for AKI. Our team has implemented a provincial program, Dialyzing Wisely (DW), to monitor and report key performance and quality indicators of CRRT, aimed at implementing evidence-formed best practices and minimizing unnecessary variations in practice.[30] A key measure this program has implemented is the dose-intensity delivered to patients receiving CRRT. Currently estimates from this audit show a mean (SD) effluent rate of 27.7 mL/kg/hr (SD 15; min 11; max 91) for patients receiving CRRT. This would imply there are currently variations in practice and that a meaningful proportion of patients are receiving less than the current guideline directed recommended dose-intensity. The Dialyzing Wisely platform provides key infrastructure to implement, measure process and outcome data, and disseminate the findings from this trial. Moreover, the findings from this trial can be immediately implemented into clinical practice, including into provincial standardized CRRT order sets, and used to establish revised dose-intensity targets for reporting in the Dialyzing Wisely program. Furthermore, if the main phase trial establishes that lower dose-intensity is acceptable and safe with no clinically meaningful differences in patient-centred or health service outcomes, the lower dose-intensity would become the current default standard and inform clinical practice guidelines for CRRT management worldwide.

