2.5 Objectives

The overall WISDOM trial program will address whether a lower CRRT dose-intensity in critically ill patients with AKI is non-inferior to standard CRRT dose-intensity and will secondarily address whether lower CRRT dose intensity will shorten total CRRT duration and improve kidney recovery compared with standard CRRT dose-intensity. This pilot trial will specifically evaluate the feasibility of lower versus standard CRRT dose-intensity.

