3.4.2 Criteria for discontinuing or modifying allocated interventions

The duration of the intervention will be until CRRT is discontinued due to any of patient death, transition to intermittent RRT (IRRT) or due to kidney recovery with no further requirement for RRT. Transition to IRRT will align with current best practices and align with local standards of care. This will generally occur following hemodynamic stabilization and weaning of vasoactive support (i.e., SOFA_{CV} score <2). Ultimate decisions about transitions to IRRT will be made by the local attending physicians. If during their ICU admission a patient has their CRRT temporarily interrupted (e.g., diagnostic imaging or other investigations; procedures or operations), once restarted, the CRRT will be prescribed according to their allocated dose-intensity. If a patient has prolonged CRRT interruption (>6 hours) (e.g., operative theatre), CRRT will be temporarily restarted at the standard dose-intensity for 6 hours to ensure a period of stabilization, then transitioned to their allocated CRRT dose-intensity, as applicable.

If patients are perceived by the treating ICU team to require a temporary increase in dose-intensity to augment acid-base/metabolic/azotemic control due to critical illness, the following actions should be followed in hierarchical order:

- i) For patients with persistent hyperkalemia, defined as [K+] > 5.5 mmol/L at 24 hours after randomization, the treating ICU team can lower the potassium [K+] concentration in the replacement/dialysis solutions, as per ICU-specific protocols.

- ii) For patients with persistent metabolic acidosis, defined as pH <7.25 and BE < -10 at 24 hours after randomization, the treating ICU team can add supplementary bicarbonate (HCO₃) either as a continuous infusion or bicarbonate can be added to the replacement/dialysate solutions, as per ICU-specific protocols.
- iii) For patients who are refractory to the above modifications to the prescribed CRRT or those who have persistent azotemia, defined as [urea] >30 mmol/L at 24 hours after randomization, the treating ICU team can adjust the dose-intensity to the upper limit of dose-intensity within the allocation. For example, in those patients allocated to the low dose-intensity group (target 10 mL/kg/hr), adjust the prescribed dose to 15 mL/kg/hr.

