3.5.6 Tertiary Endpoints

The WISDOM pilot trial is not designed to detect differences in patient-centred, kidney-centred or health service-specific outcomes[34], however, the following endpoints will be described: duration of RRT; transition from CRRT to IRRT; receipt of RRT at hospital discharge, 30-days and 90-days; RRT-free days at 90-days; ICU mortality; hospital mortality; 90-day mortality; a composite of major adverse kidney events (MAKE) at 30-days and 90-days; change in estimated glomerular filtration rate (baseline to 90-days); daily receipt of non-renal organ support (e.g., invasive and non-invasive mechanical ventilation; vasoactive therapy), ICU duration of stay, hospital duration of stay and re-hospitalization within 90-days. The kidney-specific outcomes, duration of hospitalization, and rates of re-hospitalization are outcomes that have been informed through patient and family preferences and priorities during engagement in our Dialyzing Wisely program.[30] For the next phase trial, the preferable patient-centred primary non-inferiority outcome

will be 90-day mortality (from enrollment) and for superiority, will be RRT-free days at 90-days (from enrollment). These outcomes will aid in the design of a larger-scale trial.

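### The supplementary repeated-measures model of dose-intensity adjusts for CRRT duration, a post-randomization variable, so its group coefficient can miss the randomized difference in delivered dose

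*Protocol*

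**What the plan says.** Section 5.1 of the protocol makes two statements about the same variable. First, the primary feasibility endpoint, "the difference in mean (SD) CRRT dose-intensity between groups, will be reported as difference in means (with 95% confidence intervals [CI"]). No covariates are named there. Later in the same paragraph, after the tests for the other endpoints, a mixed linear regression for repeated measures "will be performed, adjusted for baseline variables and CRRT duration, to evaluate dose-intensity differences by allocated group". The rank of this model is not stated, and the duration term is not defined.

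Four other places bear on what CRRT duration is:

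- Section 3.4.2: "The duration of the intervention will be until CRRT is discontinued due to any of patient death, transition to intermittent RRT (IRRT") or kidney recovery. Its length is therefore known only after randomization.
- Section 2.2, on earlier evidence about higher dose-intensity: "This would imply that lower dose-intensity may facilitate kidney recovery and earlier weaning from RRT".
- Section 2.5: the overall program "will secondarily address whether lower CRRT dose intensity will shorten total CRRT duration and improve kidney recovery".
- Section 3.5.6: "the following endpoints will be described: duration of RRT; transition from CRRT to IRRT". Duration of RRT, which is closely related, is thus listed as an outcome.

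**The concern.** Randomization makes the arms comparable at baseline. A covariate measured afterwards keeps that comparability only if allocation does not affect it. Here the protocol itself raises the possibility that allocation changes CRRT duration. A lower-dose patient with a five-day course may then differ in severity or recovery from a standard-dose patient with a five-day course. Comparing patients with equal courses is no longer the comparison that was randomized.

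The protocol's own rules also tie dose to duration, in opposite directions:

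- Under section 3.4.1 the standard-dose period lasts 12 to 24 hours from the start of CRRT, not from randomization, while section 3.5.2 targets randomization within 12 hours. Some standard-dose hours can therefore fall after randomization in the lower arm, and they weigh more in a short course.
- Under section 3.4.2 CRRT restarts at standard dose for 6 hours after an interruption of more than 6 hours. A long course has more room for such restarts.

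What is at stake is a second estimate of the delivered-dose difference that may disagree with the first, in a pilot whose purpose is to show dose separation, with no stated rule on which estimate governs.

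**Working it through.** **1. The plan's own figure.** Inputs from section 3.6: difference 10, SD 15, power 90%, alpha 0.05 (two-sided reproduces it).

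n per arm = 2 × (1.960 + 1.282)² × 15² / 10² = 2 × 10.51 × 2.25 = 47.3, rounded up to 48, so 96 in total. The stated 96 reproduces. It rests on the unadjusted comparison of two means, so the covariate question does not touch it.

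**2. Formula for the bias.** Let g be the shift in duration caused by allocation (lower minus standard) and b the within-arm slope of dose on duration, with b = rho × SD(dose) / SD(duration). Linear adjustment gives

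adjusted difference = true difference - b × g.

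If g is expressed as a shortening of s standard deviations of duration, b × g = -rho × SD(dose) × s. With a true difference of -10 this becomes -10 + rho × SD(dose) × s.

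**3. Numbers.** The documents give neither s nor rho; both are assumptions.

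| s (SD of duration) | rho | SD 15 | SD 5 |
|---|---|---|---|
| 0 | any | -10.00 | -10.00 |
| any | 0 | -10.00 | -10.00 |
| 0.2 | 0.1 | -9.70 | -9.90 |
| 0.2 | 0.3 | -9.10 | -9.70 |
| 0.5 | 0.3 | -7.75 | -9.25 |
| 0.5 | 0.5 | -6.25 | -8.75 |
| 0.5 | -0.3 | -12.25 | -10.75 |

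Example: 15 × 0.3 × 0.5 = 2.25, and -10 + 2.25 = -7.75.

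**4. Check in a mixed model.** Daily doses were simulated with a random intercept per patient, 50 patients per arm, between-patient SD 15 and within-patient SD 5. Durations were log-normal with a mean of 5.4 days, from section 2.3 ("2,790 CRRT-days; average 5.4 days per patient"), and an assumed SD of 0.6 on the log scale; shifts are in SDs of log duration. There were 60 replicates, with Monte Carlo SE of 0.3 to 0.4.

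| Shift | rho | Without duration | With duration |
|---|---|---|---|
| 0 | 0.3 | -9.9 | -9.8 |
| 0.3 | 0 | -10.0 | -10.0 |
| 0.3 | 0.3 | -9.8 | -8.8 |
| 0.5 | 0.5 | -10.2 | -7.0 |

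Bias appears only when both links are present. On this scale a shift of 0.5 takes the mean course from 5.4 to about 5.4 × exp(-0.5 × 0.6) = 4.0 days.

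**5. Is a dose-duration link plausible?** Suppose 12 hours at 27.5 mL/kg/hr (mid-range of standard) fall after randomization and are counted, and the patient is otherwise at 12.5 (mid-range of lower). The lower-arm average is then:

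- 2 days: (12 × 27.5 + 36 × 12.5) / 48 = 16.3
- 5.4 days: (12 × 27.5 + 117.6 × 12.5) / 129.6 = 13.9
- 10 days: (12 × 27.5 + 228 × 12.5) / 240 = 13.3

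This makes b negative, which exaggerates the separation if the lower arm has shorter courses. If sicker patients have both longer courses and higher delivered doses, b is positive and the separation is understated. The sign is therefore not known in advance.

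**The case against.** **The model is not the primary analysis.** A reader might infer that the primary result is biased. The documents do not support that: section 5.1 reports the primary endpoint as an unadjusted difference in means, and the sample size is built on the same comparison. This objection stands in full.

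**Bias is a possibility, not a fact.** A reader might also infer that the adjusted coefficient is bound to be wrong. It is wrong only if allocation shifts duration and duration is related to dose within arm. Section 2.2 says that the lower dose may help, section 2.5 asks whether it does, and section 3.5.6 says that the pilot is not designed to detect such differences. This also stands.

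**The effect may be small.** With 50 per arm and SD 15, the 95% CI half-width is 1.96 × 15 × √(2/50) = 5.9 mL/kg/hr, wider than any bias in the table. It is also tempting to show the coefficient moving across 10. But 10 is the minimum difference the trial is sized to detect, not a pass mark for this coefficient, and any such example depends on assumed inputs. That stands, although a larger sample would not remove the bias.

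**The term may mean day on CRRT.** In a model of daily doses that would be an ordinary time term, and the objection would be much weaker. The wording does not settle it. Sections 2.2 and 2.5, however, use the phrase for the total course, and section 5.1 lists it as an adjustment covariate beside the baseline variables. Section 6.1 foresees a detailed statistical analysis plan that could define the term, but the protocol has already named the covariate. This lowers the rank of the point without removing it.

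**Conclusion.** The point holds for the supplementary mixed model only. As written, that model conditions on a variable that is settled after randomization and that the program thinks treatment may change. Its group coefficient is therefore in general not the randomized difference in delivered dose. The direction and size cannot be fixed from the protocol. Under the assumptions shown, a true -10 becomes anything from -12.25 to -6.25 at SD 15, with one third of that bias at SD 5, and no bias if either link is absent. The difference in means with its 95% CI is untouched, and the sample size of 96 stands. Should-fix, not must-fix.

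**What to change.** In section 5.1:

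- Remove CRRT duration from the model's covariates, and adjust only for baseline variables and site, the stratification factor in section 4.1.
- If a time term is intended, define it as day since randomization, with a group-by-day term if wanted.
- State that the difference in means with 95% CI is the primary analysis and that the mixed model is supplementary.
- Report CRRT duration by arm as an outcome, next to the duration of RRT already listed in section 3.5.6.

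This changes a few words in the protocol, carried into the statistical analysis plan. It needs no new data, and the sample size does not change.
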